## 5.2 Pharmacokinetic Evaluation (if applicable) NA

## 5.3 Safety Evaluations

The Co-PIs will review any questionable situation immediately; the research team will review all data collections weekly.

The MPIs will regularly monitor the study and data collection procedures and meet with the EI staff to review the protocols for safety and confidentiality. Drs. [name] and [name] will constantly monitor mothers whose depressive symptoms worsen and will arrange for immediate assessment if needed.

## 6. STATISTICAL CONSIDERATION

Researchers will conduct descriptive analyses including means, standard deviation and/or frequencies. Our sample size of 8 mothers does not allow us to test pre/post changes. Nonetheless, this descriptive information will give us an initial sense of the feasibility and efficacy of the LENA intervention.

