## 2. STUDY OBJECTIVE

This project seeks to test the efficacy of this type of maternal-child focused intervention, using the LENA intervention embedded in EI to help mothers enhance their child-centered speech and reciprocal communication.

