### 2.1 Primary Objective

The primary objective of the study is to test the feasibility and initial efficacy of embedding a language pedometer, the Language ENhancement Assessment/Intervention system (LENA) into Early Intervention (EI) to teach mothers to increase child-centered speech and reciprocal communication.

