### 2.2 Secondary Objective - NA

## 3. INVESTIGATIONAL PLAN (brief overview)

### 3.1 Study Design

Type of design: Single group assignment, pre-/post-intervention

Provide brief overview of the study phases:

- Screening: screening for eligibility
- Enrollment/Baseline: obtaining consent and conducting Time 1 outcome measures prior to intervention
- Intervention: study intervention using the LENA
- Post-test/Analysis: Time 2 outcome measures after intervention and analysis

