### 3.2 Allocation to Treatment Groups and Blinding (if applicable): NA

**3.3 Study Duration, Enrollment and Number of Subjects** 10 subjects will participate in the study. Each subject's participation will last approximately 2 months. The entire study is expected to last 12 months.

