### 6.2 Secondary Endpoint - NA

### 6.3 Statistical Methods

Researchers will conduct descriptive analyses including means, standard deviation and/or frequencies. Our sample size of 8 mothers does not allow us to test pre/post changes. Nonetheless, this descriptive information will give us an initial sense of the feasibility and efficacy of the LENA intervention.

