### 6.4 Sample Size and Power

The sample size of 10 mothers is adequate to examine initial feasibility.

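### The sole stated objective includes testing initial efficacy, but Sections 6 and 6.3 say 8 mothers cannot be tested and then read efficacy from means and SDs with no interval

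*Combined protocol and SAP*

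**What the plan says.** Section 2 opens with efficacy alone: "This project seeks to test the efficacy of this type of maternal-child focused intervention". Section 2.1, which the synopsis repeats, is broader: "The primary objective of the study is to test the feasibility and initial efficacy of embedding a language pedometer". There is nothing below it: "2.2 Secondary Objective - NA". The design has no comparator: "Type of design: Single group assignment, pre-/post-intervention".

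Sections 6 and 6.3 carry the same text. They plan means, standard deviations and frequencies, and give the reason for going no further: "Our sample size of 8 mothers does not allow us to test pre/post changes". They then add that "this descriptive information will give us an initial sense of the feasibility and efficacy of the LENA intervention". No confidence interval or standard error is mentioned anywhere in the document. The synopsis also limits the analysis to description, on the grounds of small size and exploratory questions.

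The number of mothers differs between sections. Sections 6 and 6.3 have 8. Section 3.3 says "10 subjects will participate in the study", the synopsis also gives 10, and Section 6.4 says "The sample size of 10 mothers is adequate to examine initial feasibility".

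Section 5.1 and the synopsis name change in LENA Adult Word Count as the primary measure.

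**The concern.** Three statements do not fit together: the objective is to test efficacy, the sample cannot be tested, and the results will nevertheless say something about efficacy. At least one has to change.

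The middle statement matters most, because it is the plan's justification for the analysis. If testing were impossible, nothing beyond means and SDs could be asked for. If the sample is merely imprecise, the usual answer is to show how imprecise, with an interval. As written, a reader would see a mean change and an SD. The SD describes how much mothers differ from one another. It does not say how far the mean could be from the true value.

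What is at stake is what the study may conclude. A mean rise in Adult Word Count could be reported as initial evidence of efficacy, from an uncontrolled comparison, without showing whether the data are also compatible with no change or with a fall.

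**Working it through.** **Figure to reproduce.** There is none. Section 6.4 gives a sample size without a significance level, power, effect size, SD or allowance for dropout.

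**Inputs.** n = 8 (Sections 6 and 6.3) and n = 10 (synopsis, Sections 3.3 and 6.4). Assumed, because the plan gives no values: two-sided 5% level, roughly normal changes, and a mean change d expressed in SDs of the within-mother change.

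**Step 1: can 8 pairs be tested?** If all n changes go the same way, the exact two-sided sign or signed-rank p-value is 2/2^n.
- n = 8: 2/256 = 0.0078
- n = 10: 2/1024 = 0.0020

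Both are below 0.05, so a test exists at either size.

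**Step 2: how precise is the mean change?** The 95% half-width, in SDs of the change, is t(0.975, n−1)/√n.
- n = 8: 2.365/2.828 = 0.84
- n = 10: 2.262/3.162 = 0.72

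**Step 3: what could a paired t-test detect?** Power comes from the noncentral t distribution with n−1 degrees of freedom and noncentrality d√n.

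| Mean change d (SD of change) | Power, n = 8 | Power, n = 10 |
|---|---|---|
| 0.5 | 23% | 29% |
| 0.8 | 50% | 62% |
| 1.0 | 68% | 80% |

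Solving for 80% power gives d = 1.16 at n = 8 and d = 1.00 at n = 10.

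**Step 4: which test do these figures describe?** They belong to the paired t-test and should not be quoted for an exact test. At two-sided 5% the sign test needs 8 of 8 mothers in one direction, because 7 of 8 gives 2 × 9/256 = 0.070. At d = 1.16 the chance that one mother improves is Φ(1.156) = 0.876, so the power is about 0.876^8 = 35%. At n = 10 and d = 1.00, the sign test (9 or more of 10) has about 51%. The exact signed-rank test has about 74% and 78%.

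**Step 5: could a reader recover the interval?** Only if the SD reported is that of the within-mother change. Section 5.1 defines the outcomes as changes, but Sections 6 and 6.3 do not say whether the means and SDs are of changes or of each time point. From the two time-point SDs alone, the paired interval cannot be rebuilt without the correlation between them.

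**The case against.** The strongest defence is that the plan is modest. Section 2.1 and the synopsis speak of feasibility and *initial* efficacy, Section 6.4 justifies the sample for feasibility only, and the synopsis calls the questions exploratory and the analysis descriptive. Sections 6 and 6.3 offer no more than a first impression. Read in context, the sentence about not being able to test may simply mean that the sample is too small for useful inference, and 23% power at 0.5 SD supports that choice. All of this stands, and it limits the weight of the point. It does not reconcile the objective with the analysis, and it does not explain why an interval is left out.

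Several stronger readings are tempting but not supported:

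- *A reader might infer that efficacy is the only objective.* Section 2 taken alone reads that way, but Section 2.1 and the synopsis include feasibility.
- *A reader might infer that an ineffective intervention would look favourable about half the time.* That requires any mean above zero to count as favourable, which the plan never says, and no drift over time. In a design without controls, an assumed drift of 0.2 SD upward or downward moves the 0.50 to Φ(0.2 × √8) = 0.71 or to 0.29 at n = 8.
- *A reader might add that with six outcomes some favourable movement is nearly certain.* The figure 1 − 0.5^6 = 98% assumes six independent, interchangeable outcomes. Section 5.1 and the synopsis put Adult Word Count first.
- *A reader might want a success rule such as 7 of 8 or 9 of 10 mothers improving.* If 80% truly improve, the power of that rule falls from 50% to 38% as n rises. Parts of the protocol (Sections 4.8, 4.9 and 11) are in the past tense, so a cut-off set now might not be prospective.

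**Conclusion.** The point holds as a matter of wording and precision. The objective promises a test of initial efficacy, the statistical section says none is possible, and the conclusion still refers to efficacy with no interval around the estimate. The claim that 8 mothers cannot be tested is literally untrue; the accurate statement is that precision is low. In size, the 95% interval is about ±0.84 SD of the change with 8 mothers or ±0.72 SD with 10, and 80% power is reached only at about 1.16 SD or 1.00 SD.

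These figures assume a two-sided 5% level, approximately normal changes, and complete pairs for all 8 or 10 mothers. The documents give no SD for Adult Word Count, so the figures cannot be turned into words per day. The documents do not support reading the plan as making a confirmatory claim. An interval would show precision only; with a single group it could not attribute any change to LENA.

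**What to change.** - **Sections 2 and 2.1 and the synopsis objective:** replace the promise to test efficacy or initial efficacy with an aim to describe change, and keep feasibility. Align the efficacy wording in the synopsis design row and in Section 5.1.
- **Sections 6 and 6.3:** replace the sentence on not being able to test with, for example: *The sample gives low precision. At a two-sided 5% level a paired t-test has 80% power only for a mean change of about 1.16 SD of the change with 8 mothers (1.00 SD with 10), and the 95% confidence interval extends about 0.84 SD (0.72 SD) either side of the mean change.* Keep the figure that matches the final number of mothers.
- **Same sections:** report the mean within-mother change in Adult Word Count, its SD, the number of mothers with both values, and the 95% confidence interval.
- **Same sections:** delete *and efficacy* from the closing sentence, so that no change is attributed to LENA in this uncontrolled design.
- **Sample size:** reconcile 8 mothers (Sections 6 and 6.3) with 10 (synopsis, Sections 3.3 and 6.4), and say whether the smaller number is those analysed.

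The cost is wording in a few places and one line of analysis, with no new data. The downside is that the efficacy claim becomes weaker.

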### 6.1 Primary Endpoint

The primary endpoint is 6 weeks after the LENA intervention.

### 6.2 Secondary Endpoint - NA

### 6.3 Statistical Methods

Researchers will conduct descriptive analyses including means, standard deviation and/or frequencies. Our sample size of 8 mothers does not allow us to test pre/post changes. Nonetheless, this descriptive information will give us an initial sense of the feasibility and efficacy of the LENA intervention.

### 6.4 Sample Size and Power

The sample size of 10 mothers is adequate to examine initial feasibility.

### 6.5 Interim Analysis - NA

## 7. STUDY INTERVENTION (drug, device or other intervention details)

Mothers will run the Language Enhancement Assessment/intervention system with their young child for the first time for one day up to 16 hours and will mail the recorder back to the research team. Researchers will provide an initial feedback session, which will include reviewing the LENA visual output from the previous recording and how mothers can access the output on their own for future recordings. Mothers will independently use the LENA system and access the output on their own for 5 additional recordings over 5 weeks, again mailing each recorder back to the team after the receiving it again from the research team once the recording is uploaded to the LENA system.

## 8. STUDY INTERVENTION ADMINISTRATION(if applicable)

NA

## 9. SAFETY MANAGEMENT

Mothers will be observed for fatigue and encouraged to tell the research team that they are too tired to continue. In such cases, the data collection session will be terminated and a follow-up session scheduled. Our preliminary and ongoing studies have shown that some mothers may not read well and become fatigued. Questionnaires are written clearly and simply and have been tested with mothers with limited literacy. Questionnaires will be read orally to all mothers if they wish. Visual aides in the form of printed response sets will be given to mothers so that they can point to the desired responses.

Plans to ensure necessary intervention in emotional distress: Research staff will follow a protocol for emergency situations and the project will adhere to the state legal statutes governing mandated reporting of suspected child abuse. If, during any contact with a project staff member, a mother expresses suicidal ideation, or is so immobilized by symptoms that she or her child are in danger, or is in danger because of domestic violence, the research staff member will assess the mother, contact the PI's and Project Coordinator, and, if with the mother, will remain with her until a safe resolution has been reached, i.e., immediate referral to a community resource and/or involvement of supporters who can continue to ascertain the safety of the mother and infant/toddler after the team member leaves the premises.

The decision about which resources to refer the mother will be made in consultation with the PI's and Co-Investigator [name], a psychiatrist specializing in women's mood disorders and with the mother's permission, the CDSA Service Coordinator. The project will maintain a log of all incidents requiring emergency, immediate response, or referral, and will report exceptional incidents to the IRB as appropriate. [name], [name], [name], the Project Coordinator ([name]) and [name] are licensed mental health professionals familiar with depressive symptoms and emergency situations. The protocol will ensure that one or more of these research team members is on call for such situations. At the last contact with the study, mothers will receive a mental health resource referral list and with their permission, the CDSA Service Coordinator will be consulted as well to assure continuity. A review of all mothers actively in the project will be conducted in weekly research team meetings with the PI's and when needed, [name].

## 10. DATA COLLECTION AND MANAGMENT

Mothers will be told that all data will be separated from the consent forms and identified by a number and that only the research team will have access to the names and numbers. The identity of participants will not be divulged to anyone except in the instance that the mother cannot be located through the contacts she has provided. In that instance, Durham CDSA will be contacted for information about the mother's current location and mothers will give the project written permission for this exception as part of their study consent. Permission to Contact forms will be kept in a locked file in a locked office at the Durham CDSA program until retrieved by a research team member. All study data will be kept in a locked office and a locked file at the FPG office. Data management procedures will include initial data cleaning, double keying, error checking and error corrections, and data validation prior to analysis. Data will be reported in aggregate form only, without identifying information by individual or site. All personnel will be trained to maintain security and confidentiality of the data. The mothers will be apprised of these precautions.

## 11. RECRUITMENT STRATEGY

Interest letters describing the study will be mailed from our Part C research partner to mothers in April -June 2018. Interested mothers will contact the research team by phone or email to schedule a time to screen them for eligibility for the study. Screenings will be done via phone by a research team member who will administer the PHQ-9 and collect demographic information. Researchers will give mothers opportunities to ask questions about the nature of their participation. If mothers speak Spanish,

materials will be available in Spanish and the screening process will be completed by a research team member who is bilingual in English and Spanish.

Although our original inclusion criteria included individuals with a PHQ-9 score greater than 8, we were not able to include recruit enough mothers who met this criterion, so we dropped it from our eligibility criteria.

## 12. CONSENT PROCESS

For eligible mothers, researchers will schedule a home visit to go over enrollment procedures (i.e., complete consent forms). Researchers will give mothers opportunities to ask questions about the nature of their participation. If mothers speak Spanish, materials will be available in Spanish and the consent process will be completed by a research team member who is bilingual in English and Spanish.

## 13. PLANS FOR PUBLICATION

We have two papers in progress we will submit for publication.

## 15 APPENDIX

Nothing to report.
